6.2 MPDL3280A Expected or Potential Toxicities

Any toxicities associated or possibly associated with MPDL3280A treatment should be managed according to standard medical practice. No reduction of the MPDL3280A dose will be allowed (Section 5.7.1.2). Additional tests, such as autoimmune serology or biopsies, may be used to determine a possible immunogenic etiology of a toxicity.

Most immune-related adverse events (irAEs) observed with immunomodulatory agents have been mild and self-limiting; however, such events should be recognized early and treated promptly to avoid potential major complications. The primary approach to managing Grade 1-2 irAEs is supportive and symptomatic care. In the case of recurrent Grade 2 events or in severe cases, immune-related toxicities may be acutely managed with topical corticosteroids, systemic corticosteroids, or tumor necrosis factor alpha (TNF- α) inhibitors, as well as delay or permanent discontinuation of MPDL3280A. There is no available antidote for MPDL3280A, and as a result, discontinuation of MPDL3280A may not have immediate therapeutic effect. In severe cases, immune-related toxicities may be acutely managed with topical corticosteroids, systemic corticosteroids, or TNF- α inhibitors. In addition, consideration may be given to holding rociletinib doses temporarily even if the toxicity is not attributed to rociletinib.

Management of possible infusion reactions, gastrointestinal toxicity (including colitis), hepatotoxicity (including hepatitis and elevated transaminases), dermatologic toxicity, hypothyroidism, pulmonary toxicity, pericardial and pleural effusions, pancreatic toxicity, and ocular toxicity are presented in the following sections. See also Appendix F for precautions for anaphylaxis.

6.2.1 Management of Infusion Reactions

The management of infusion-related reactions will be according to severity as follows:

Description	Management
Grade 1 (mild)	• Reduce infusion rate to half the rate being given at the time of event onset;
	• Once the event has resolved, the Investigator should wait for 30 minutes while delivering the infusion at the reduced rate;
	• If tolerated, the infusion rate may then be increased to the original rate.
Grade 2	Interrupt MPDL3280A infusion;
(moderate)	• Administer aggressive symptomatic treatment;
OR	• Restart only after the symptoms have adequately resolved to baseline grade;
Flushing, fever, throat pain	• The infusion rate at restart should be half of the infusion rate that was in progress at the time of the onset of the infusion-related reaction.
Grade 3 or 4	• Interrupt infusion;
(severe or life-threatening	• Initiate aggressive resuscitation and supportive measures;
[see Appendix F])	• Do not re-administer MPDL3280A;
	• Manage patient as clinically indicated until the event resolves.

 Table 11: Management Guidelines for Infusion-Related Reactions during Cycle 1

6.2.2 Management of Gastrointestinal Toxicity

Immune-mediated colitis has been associated with the administration of MPDL3280A. Treatment guideline is summarized in Table 12.

Table 12:	Management	Guidelines for	Gastrointestinal	Toxicity ((Diarrhea)	

Description	Management			
Grade 2 (4-6 stools/day over	• Hold MPDL3280A and discontinue NSAIDS (or other medication known to exacerbate colitis).			
baseline) < 5 days	Investigate for etiology.			
	• Restart MPDL3280A once at baseline stool frequency.			
Grade 2 (4-6 stools/day over	• Hold MPDL3280A and discontinue NSAIDS (or other medication known to exacerbate colitis) while etiology is being investigated.			
baseline) > 5 days	Consider referral to a gastroenterologist.			
	• Administer anti-diarrheal agent (eg, Imodium).			
	• Consider oral budesonide, mesalamine, or 10 mg oral prednisone equivalent per day.			
	• Restart MPDL3280A once at baseline stool frequency.			
Grade \geq 3 (\geq 7 stools/day over	• Hold MPDL3280A and discontinue NSAIDS (or other medication known to exacerbate colitis).			
baseline) with peritoneal	• Rule out bowel perforation.			
signs, neus, or iever	• Consider administering prednisone 60 mg/day or equivalent (oral budesonide or methylprednisolone IV).			
OR	• Taper steroids over 1 month.			
Abdominal pain Blood or mucus in stool	• Restart MPDL3280A if diarrhea is resolved as confirmed by sigmoidoscopy or colonoscopy and systemic steroid dose is ≤ 10mg oral prednisone equivalent per day			
	• Permanently discontinue MPDL3280A for life-threatening immune-related diarrhea or colitis.			

IV, intravenous; NSAID, nonsteroidal anti-inflammatory drugs; TNF, tumor necrosis factor.

If the event is of significant duration or magnitude or is associated with signs of systemic inflammation or acute phase reactants (eg, increased C-reactive protein or platelet count or bandemia), it is recommended to do the following:

- Perform sigmoidoscopy (or colonoscopy, if appropriate) with colonic biopsy with three to five specimens for standard paraffin block to check for inflammation and lymphocytic infiltrates for confirmation of the diagnosis of colitis. If possible, one or two biopsy specimens should be snap frozen and stored.
- Perform laboratory tests to rule out alternate etiology (ie, white blood cells [WBCs] and stool calprotectin).

6.2.3 Management of Hepatotoxicity

Immune-mediated hepatitis has been associated with the administration of MPDL3280A. Eligible patients must have adequate liver function, as manifested by measurements of total bilirubin and hepatic transaminase, and liver function will be monitored throughout study treatment.

While on this study, patients presenting with right upper-quadrant abdominal pain and/or unexplained nausea or vomiting should have LFTs performed immediately and reviewed before administration of the next dose of study drug.

If LFTs increase, neoplastic, concurrent medications, viral hepatitis, and toxic etiologies should be considered and addressed, as appropriate. Imaging of the liver, gall bladder and biliary tree should be performed to rule out neoplastic or other causes for increased LFTs. Anti-nuclear antibody, perinuclear anti-neutrophil cytoplasmic antibody, anti-liver kidney microsomal antibodies, and anti-smooth muscle antibody tests should be performed if an autoimmune etiology is considered.

Patients with LFT abnormalities should be managed according to Table 13.

Description	Management
AST/ALT (> ULN to 3 × ULN) with total bilirubin < 2 × ULN	• Continue with the standard monitoring plan (ie, LFTs every 3 weeks before dosing).
AST/ALT (> 3 × ULN to < 10 × ULN) with total bilirubin < 2 × ULN	• Continue MPDL3280A. Monitor LFTs at least weekly. Consider referral to a hepatologist.
$AST/ALT > 10 \times ULN$	• Hold MPDL3280A;
	• Consider administering IV steroids for 24-48 hours (prednisone 60 mg/day equivalent) followed by oral prednisone (or equivalent) taper over 2-4 weeks;
	 If LFT results do not decrease within 48 hours after initiation of systemic steroids, addition of an alternative immunosuppressive agent (eg, mycophenolate or TNF-α antagonist) to the corticosteroid regimen may be considered;
	• Monitor LFTs every 48-72 hours until decreasing and then follow weekly;
	 Restart MPDL3280A after discussion with the Medical Monitor if AST/ALT ≤ 3 × ULN with bilirubin < 2 × ULN and steroid dose is ≤ 10 mg oral prednisone equivalent per day;
	• Permanently discontinue MPDL3280A for life-threatening immune- related hepatic events.

 Table 13:
 Management Guidelines for Hepatotoxicity (LFT Abnormalities)

Table 13: Management Guidelines for Hepatotoxicity (co	continued)	
--	------------	--

AST/ALT \ge 3 × ULN with bilirubin > 2 × ULN	 Hold MPDL3280A; Consult hepatologist; Consider administering IV steroids for 24-48 hours (prednisone 60 mg/day equivalent) followed by oral taper over 1 month;
	 If LFT results do not decrease within 48 hours after initiation of systemic steroids, addition of an alternative immunosuppressive agent (eg, mycophenolate or TNF-α antagonist) to the corticosteroid regimen may be considered;
	• Monitor LFTs every 48-72 hours until decreasing and weekly after;
	 Restart MPDL3280A after discussion with the Medical Monitor if AST/ALT ≤ 3 × ULN with bilirubin < 2 × ULN and steroid dose is ≤ 10mg oral prednisone equivalent per day.

ALT, alanine aminotransferase; AST, aspartate aminotransferase; IV, intravenous; LFT, liver function test; TNFα, tumor necrosis factor alpha; ULN, upper limit of normal.

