	Dose modification guidelines for rociletinib and MPDL3280A are described in Section 5.7.

Concomitant Medications	Concomitant therapy includes any prescription or over-the-counter medications or preparations used by a patient from 28 days prior to the first dose of study treatment through 28 days after the last dose of study treatment, or the date of administration of subsequent anticancer therapy, whichever is earlier. All concomitant medications should be reported to the Investigator and recorded. Guidelines for use of concomitant medications are detailed in Section 7.							
W/4h dwarral								
Criteria	 Consent withdrawal at the patient's own request or at the request of their legally authorized representative; 							
	• Clinical disease progression where the Investigator believes that the patient will not continue to benefit from study treatment (Note: patients will be permitted to continue study treatment after a radiographic progression [Appendix A and Appendix B] if the benefit-risk ratio is judged to be favorable and continued treatment is approved by the Medical Monitor);							
	• Any event, adverse or otherwise, that, in the opinion of the Investigator, would pose an unacceptable safety risk to the patient;							
	• An intercurrent illness that, in the opinion of the Investigator, would affect assessments of the clinical status to a significant degree and requires discontinuation of therapy;							
	• A positive pregnancy test at any time during the study;							
	• Non-compliance as described in Section 5.5;							
	Investigator decision.							
	In addition, the Sponsor may discontinue the study early for any of the reasons noted in Section 12.6.							
Study Procedures	The Screening Period will be 28 days prior to the first dose of study treatment. Some assessments are required to be performed within shorter windows (eg, 7 or 14 days) prior to the first dose of study treatment (see Table 1). A mandatory baseline biopsy will be collected within 60 days prior to first dose of study treatment.							
	The Treatment Period will consist of 21-day treatment cycles. In Phase 1 only, there will be an additional 7-day Run-in-Period of rociletinib monotherapy. Clinic visits are scheduled on Day 1 of each cycle and more frequently during Cycle 1 (see Table 1).							

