3.2.1 Dose-Limiting Toxicity

Determination of DLTs will be made during the first 21 days of combination treatment with rociletinib and MPDL3280A (ie, during Cycle 1 after the rociletinib Run-in-Period) in the Dose Finding Phase. A DLT is defined as a clinically significant AE or laboratory abnormality assessed as at least related to the study drug (rociletinib and/or MPDL3280A), unrelated to disease progression, and that meets any of the following criteria:

Cytopenia:

- Grade 4 neutropenia persisting for more than 7 days;
- Febrile neutropenia, defined as an absolute neutrophil count (ANC) < 1000/mm³ and a single temperature of > 38.3°C (101°F);
- Grade 4 thrombocytopenia persisting for more than 7 days or thrombocytopenia with clinically significant bleeding (ie, bleeding that requires blood or platelet transfusion or other medical intervention, or that may cause disability or death, such as cerebral hemorrhage).

Organ Toxicity:

• Grade \geq 3 symptomatic hepatic toxicities lasting for > 48 hours, or Grade \geq 3 asymptomatic hepatic toxicities lasting for > 7 days with the following exception:

- For patients with Grade 2 Alkaline phosphatase (ALP) abnormality at baseline, an increase to > 8 × the upper limit of normal (ULN) lasting > 48 hours (if symptomatic) or > 7 days (if asymptomatic) will be considered a DLT.
- Grade \geq 3 nonhematologic, nonhepatic organ toxicity, with the following exceptions:
 - **DLT Toxicity Exceptions**
 - Grade 3 nausea, vomiting, or diarrhea that resolves to Grade ≤ 1 within 7 days after starting appropriate supportive therapy (see Section 6.2.2);
 - Grade ≥ 3 asymptomatic or mildly symptomatic rash that can be adequately managed with supportive care (see Section 6.2.4) or symptomatic rash that resolves to become asymptomatic and/or Grade ≤ 2 within 7 days of appropriate supportive therapy;
 - Grade \geq 3 fatigue that resolves to Grade \leq 2 within 7 days;
 - Grade 3 arthralgia that can be adequately managed with supportive care or that resolves to Grade ≤ 2 within 7 days;
 - Grade 3 autoimmune thyroiditis or other endocrine abnormality that can be managed by endocrine therapy and that would not necessitate initiation of systemic corticosteroids;
 - Grade 3 fever (in the absence of any clinically significant source of fever) that resolves to Grade ≤ 2 within 7 days with supportive care;
 - Grade 3 laboratory abnormality that is asymptomatic and deemed by the Investigator to be not clinically significant;

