5.7.2 Phase 1 – Run-in-Period

Rociletinib monotherapy will be administered orally BID during the 7-day Run-in-Period. Dose reductions of rociletinib during the Run-in-Period are not allowed for reasons other than a DLT. Dose delays of rociletinib for up to 48 hours for toxicity management is allowed. Any patient who experiences an AE(s) that requires either a delay of treatment for more than a total of 48 hours or a dose reduction during the 7-day Run-in Period of rociletinib monotherapy will not be eligible for combination therapy. Such a patient will only receive monotherapy rociletinib for the duration of participation in the study.

5.7.3 Phase 1 – Cycle 1

The first dose of MPDL3280A at 1200 mg will be administered by IV on C1D1. Dose reductions of rociletinib are not allowed for reasons other than a DLT or a decision by the CSC based on emerging safety data. Dose delays of rociletinib are not allowed for reasons other than toxicity. Patients are eligible for safety and DLT evaluation of the cohort if they receive at least 75% of the planned total dose of each study drug within Cycle 1 or they experience a DLT at any time during Cycle 1.

5.7.4 Beyond DLT Assessment (Phase 1 – Cycle 2+ and Phase 2 – All Cycles)

For patients who experience a toxicity that is equivalent to a DLT – If the toxicity is assessed as being related to rociletinib, the next dose of rociletinib should be held until resolution of the toxicity to Grade 1 or to the baseline level (if severity > Grade 1 at baseline) and then reduced to the next dose level of rociletinib (Table 7), unless permanent discontinuation of rociletinib is required per toxicity management guidelines of the protocol (Sections 6.1 and 6.3). If the toxicity is assessed as being related to MPDL3280A, the next dose of MPDL3280A should be held until the toxicity has resolved to Grade 1 or to the baseline level (if severity > Grade 1 at baseline), unless permanent discontinuation of MPDL3280A is required per toxicity management guidelines of the protocol (Sections 6.2 and 6.3). In addition, because there is no available antidote for MPDL3280A and discontinuation of MPDL3280A may not have immediate therapeutic effect, consideration may be given to holding rociletinib doses temporarily even if the toxicity is not attributed to rociletinib.

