6 MONITORING AND MANAGEMENT OF EXPECTED OR POTENTIAL TREATMENT-RELATED TOXICITY

In general, toxicities should be managed with supportive care and with dose modifications for each of the study drugs (Section 5.7) according to attribution of the toxicity. Certain toxicities may be more likely to occur with rociletinib or MPDL3280A, and some toxicities may be overlapping. This section provides guidance on the monitoring and management of expected or potential toxicities associated with rociletinib or MPDL3280A or both rociletinib and MPDL3280A.

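### For a persistent, clinically significant Grade ≥3 AST/ALT rise below 10 × ULN attributed to MPDL3280A alone, Table 13 says continue while Section 5.7.4 says hold the next dose

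*Combined protocol and SAP*

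**What the plan says.** Section 6.2.3 directs that LFT abnormalities be managed by Table 13. In the row for AST/ALT above 3 and below 10 × ULN with total bilirubin below 2 × ULN, the action is "Continue MPDL3280A. Monitor LFTs at least weekly. Consider referral to a hepatologist". The row has no limit on grade, duration, symptoms or clinical significance. Table 13 holds MPDL3280A in two other situations: AST/ALT above 10 × ULN, and AST/ALT at or above 3 × ULN with bilirubin above 2 × ULN.

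Section 5.7.4 covers Phase 1 from Cycle 2 and all Phase 2 cycles. For a toxicity equivalent to a DLT and related to MPDL3280A, it says "the next dose of MPDL3280A should be held until the toxicity has resolved to Grade 1 or to the baseline level". Its one exception for the toxicity guidelines is "unless permanent discontinuation of MPDL3280A is required per toxicity management guidelines of the protocol (Sections 6.2 and 6.3".

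Section 3.2.1 sets the DLT threshold. The lead-in is "A DLT is defined as a clinically significant AE or laboratory abnormality assessed as at least related to the study drug". The hepatic criterion requires Grade ≥3, lasting more than 48 hours if symptomatic; the other limb is "asymptomatic hepatic toxicities lasting for > 7 days with the following exception" (the exception concerns alkaline phosphatase).

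Three other statements bear on which rule applies. The synopsis says "Dose modification guidelines for rociletinib and MPDL3280A are described in Section 5.7". The opening of Section 6 refers, in general terms, to "dose modifications for each of the study drugs (Section 5.7) according to attribution of the toxicity". The opening of Section 6.2 lists, for recurrent Grade 2 or severe immune-related events, corticosteroids or TNF-α inhibitors "as well as delay or permanent discontinuation of MPDL3280A".

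**The concern.** Immune-mediated hepatitis is a named risk of MPDL3280A, and Section 5.7.4 notes that the drug has no antidote, so an infusion cannot be taken back. A site that finds abnormal LFTs is sent to Table 13. If the value falls in the middle band, the table tells the site to carry on dosing. Nothing in that row warns that a Grade ≥3 event may have become DLT-equivalent through persistence and clinical significance, at which point Section 5.7.4 says to hold. Two sites could treat the same patient differently, each following the protocol. This affects patient safety and the consistency of MPDL3280A exposure and dose-hold data across sites.

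**Working it through.** The plan states no figure to reproduce. The check is whether one patient can meet both triggers at one infusion, and when.

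**Which rules apply to the case**

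| Condition | Table 13, middle row | Section 5.7.4 with Section 3.2.1 |
|---|---|---|
| AST/ALT | >3 to <10 × ULN | Grade ≥3 |
| Bilirubin | <2 × ULN | no condition |
| Duration | no condition | >48 h symptomatic; >7 days asymptomatic |
| Clinically significant | no condition | required |
| Attribution | not stated (MPDL3280A section) | related to MPDL3280A |
| Action | continue | hold next dose until Grade 1 or baseline |

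Bilirubin below 2 × ULN and AST/ALT below 10 × ULN exclude both Table 13 hold rows. Attribution to MPDL3280A alone excludes Table 18, whose rows are for toxicity attributed to both agents. A patient meeting every condition in both columns cannot be managed under both.

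**Width of the overlap**

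The protocol grades by CTCAE v4.03 but does not print the Grade 3 cut-off for AST/ALT. Call it G × ULN. The overlap runs from G to 10, so its width is max(0, 10 − G):

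- assumed G = 5: 10 − 5 = 5 × ULN
- assumed G = 8: 10 − 8 = 2 × ULN
- assumed G = 10: 10 − 10 = 0

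The Table 18 liver row gives 10 × ULN as a separate limit for patients with hepatic metastases, alongside Grade ≥3 for others. That suggests G is below 10, so the overlap is not empty.

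**When the conflict first appears**

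Table 1 schedules serum chemistry, which includes AST and ALT, on Day 1 of each cycle and not on Days 4, 8 or 15 of Cycle 1. Table 13 calls for at least weekly LFTs in this band.

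- Asymptomatic rise first seen pre-dose on an infusion day (day 0): 0 documented days, so Section 5.7.4 is not shown to be triggered at that infusion. With weekly tests on days 7, 14 and 21, the first beyond 7 days is day 14. The next infusion is day 21. If the rise persists, both rules first demonstrably apply there, one cycle after detection.
- Symptomatic rise: Section 6.2.3 asks for immediate LFTs for right upper-quadrant pain or unexplained nausea or vomiting. Counting whole days, the first interval longer than 48 hours is 3 days. A test at least 3 days before an infusion can therefore put both rules in force at that infusion.

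These timings assume no other unscheduled tests and a rise that stays in the band.

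**The case against.** The strongest reply is that the texts reconcile on an ordinary reading. Section 5.7.4 cites Sections 6.2 and 6.3 by number and yields to them only for permanent discontinuation, which implies that a continue instruction in Section 6.2 does not displace the hold. The synopsis and the opening of Section 6 both point to Section 5.7 for dose modification. Table 13 is then the entry-level guide, and Section 5.7.4 takes over once an event is DLT-equivalent. This is the better reading. But the reader must infer it, and the row the site is sent to says the opposite without a cross-reference.

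A reader might go further and infer that the Table 13 row is out of step with the whole protocol. The documents do not support that. The transaminase thresholds for events of special interest in Section 9.6 (above 3 × ULN with bilirubin above 2 × ULN, or above 10 × ULN) essentially match Table 13's two hold triggers, so the bands look deliberate. Table 18 does hold both drugs for a milder Grade ≥3 rise, but only when it is attributed to both agents, so it does not decide this case.

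A reader might also infer that sites are compelled to dose into liver injury. They are not. Both texts say what should be done. Section 5.7.4 and Table 8 permit MPDL3280A holds of up to 42 days, for toxicity or other reasons. Section 11.1 requires stopping treatment for any event the investigator judges an unacceptable risk. Section 8.4.2.2 requires investigator review of safety laboratory results before dosing. These limit the harm, but none says which instruction to follow.

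Finally, attribution to MPDL3280A alone will be hard to make while rociletinib is taken continuously; Table 3 lists a rociletinib-related serious event of raised transaminases. That makes the case rarer but does not remove it.

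**Conclusion.** The inconsistency is real and confined to one case: AST/ALT Grade ≥3 but below 10 × ULN, bilirubin below 2 × ULN, clinically significant, past the DLT duration, and attributed to MPDL3280A alone, in Phase 1 from Cycle 2 or in any Phase 2 cycle. Table 13 would dose this patient; Section 5.7.4 would hold. The balance of the text favours holding.

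Severity is low. Six conditions must coincide, investigators may hold at their discretion, and an asymptomatic rise first found pre-dose produces a demonstrable conflict only at the infusion 21 days later. The conclusion rests on a Grade 3 cut-off below 10 × ULN, which Table 18 suggests but the protocol does not print. The number of patients affected is unknown.

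**What to change.** Limit the Table 13 continue row (above 3 to below 10 × ULN, bilirubin below 2 × ULN) to events that are not DLT-equivalent under Section 3.2.1, and add: *Hepatic events equivalent to a DLT: hold MPDL3280A per Section 5.7.4.* This writes down the direction Section 5.7.4 already takes and leaves the other Table 13 rows and Section 9.6 unchanged.

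The wording change is short but must go through Section 12.7: sponsor approval, investigator agreement, IRB approval before implementation, and submission to the regulatory authorities concerned, with sites in three countries (Section 4.1). Bundling it with another amendment would keep the burden small. It may lead to a few more MPDL3280A holds. It needs no new tests and no more patients.
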